1 INTRODUCTION

This document presents the statistical analysis plan (SAP) for protocol RLY5016-207, entitled “A Randomized, Double-Blind, Placebo-controlled, Parallel Group Study of Patiromer for the Enablement of Spironolactone Use for Blood Pressure Control in Patients with Resistant Hypertension and Chronic Kidney Disease: Evaluation of Safety and Efficacy (AMBER)”.

Results obtained from the analyses outlined in this document will provide the basis of the Clinical Study Report (CSR) for this study. The statistical rationale and analysis methods specified in this document take precedence over those described in the protocol, should there be any differences.

2 STUDY OBJECTIVES AND STUDY DESIGN

2.1 Study Objectives

The objective of the study is to determine whether patiromer treatment of CKD subjects receiving spironolactone for the treatment of resistant hypertension will result in:

- More persistent use of spironolactone through prevention of hyperkalemia
- Improved blood pressure control through more persistent use of spironolactone

2.2 Study Design

This study is a randomized, double-blind, placebo-controlled, parallel group study of patiromer or placebo treatment (patiromer/placebo) in conjunction with spironolactone in subjects with resistant hypertension and CKD. Approximately 290 subjects will be randomized.

Screening for this study includes 4 visits and lasts up to 4 weeks. Subjects who meet all eligibility criteria are randomized to receive either spironolactone and patiromer or spironolactone and placebo. The active treatment period runs for 12 weeks. A follow-up visit is scheduled 2 weeks after completion of the Week 12 or Early Termination (ET) Visit.

Study periods are as follows:

- Screening Period (4 Visits)
Screening Visit 1 (S1), Screening Visit 2 (S2), Screening Visit 3 (S3) and Screening Visit 4 (S4) occur one week apart (at least 4 days but no more than 10 days). If the subject meets all eligibility criteria at the final screening visit (S4), the visit becomes the Randomization/Baseline Visit.
- Double-Blind Treatment/Observation Period (12 weeks)
At the Randomization/Baseline Visit, each subject is randomized to either spironolactone + patiromer or spironolactone + placebo, and is instructed to begin study drug on the following day, which then becomes Day 1 of the study.

The Double-Blind Treatment/Observation Period consists of 8 scheduled visits at Weeks 1, 2, 3, 4, 6, 8, 10, and 12. The intent is to observe all subjects for the entire 12 weeks of this period, whether or not they have discontinued study drug.

- Follow-up Period

[figure not shown]
Two weeks after the subject has completed either the Week 12 Visit or ET Visit, the subject returns for a Follow-up (FU) Visit.

The Schedule of Events for this study is presented in Appendix A.

The initial dose of spironolactone will be 25 mg QD for all subjects, and the initial dose of patiromer/placebo will be 2 packets QD. If a subject's blood pressure and potassium assessments allow, the dose of spironolactone will be increased to 50 mg QD at Week 3. Detailed titration rules for spironolactone and patiromer/placebo are specified in the protocol in Appendix B (patiromer/placebo) and Appendix C (spironolactone).

The overall design of the study is presented schematically below in Figure 1.

Figure 1. Study Schema

AOBP = automated office blood pressure; HBP = home blood pressure; eGFR = estimated glomerular filtration rate; K⁺ = potassium measurement; R = Randomization/Baseline (Day 0) Visit; S = Screening Visit; SBP = systolic blood pressure; W = week

- ^a Receiving at least three antihypertension drugs including diuretic. ACE inhibitors or ARBs should be included among these three antihypertensive medications, unless previously not tolerated or contraindicated (see Inclusion Criteria).
- ^b Mean (calculated by the IWRS) of two values measured at Visits S1 and S3 (or 7 to 28 days apart) during the Screening/Run-in Period.
- ^c Qualifying local laboratory K⁺ measurements of 4.3 – 5.1 mEq/L obtained at Visits S1, S3 and S4 (all measurements must be within range)
- ^d Subjects who develop hyperkalemia (K⁺ ≥ 5.5 mEq/L) that cannot be managed with blinded patiromer/placebo escalation according to the treatment algorithm will discontinue spironolactone and patiromer/placebo, but still remain in the study. Hyperkalemia may be treated using standard of care
- ^e Performed both by a designated oscillometric BP monitoring device that will automatically measure subject’s BP in triplicate after 5 minutes of sitting quietly without the aid of study staff, AOBP, and by the subject using their issued HBP device (triplicate measurements).
- ^f Two (2) weeks after the Week 12 (+ 7 days) or ET Visit (note, no subject measured office BP at this Visit). Subjects who complete the Follow-up Visit prior to 2 Weeks will receive a Follow-up Phone Call at 2 weeks (+ up to 7 days) after Week 12 or ET Visit.

Note: The reference to Appendix C for dosing is referring to the Protocol Appendix C. For subjects with study drug (spironolactone or patiromer/placebo) modifications based on BP assessments or potassium levels, an Unscheduled Visit will be conducted within 1 week after this modification unless the next scheduled visit is within 1 week of the study drug modification, in which case, the subject will return at the next scheduled visit. For all study visit windows, refer to the Schedule of Events.

2.3 Sample Size Determination

This study will randomize approximately 290 subjects, to ensure that at least 280 subjects will be available for the primary analysis. This allows for the possibility that up to 10 subjects are randomized but never take study medication. A sample size of 280 subjects has 90% power to detect a difference between treatment groups of 20% or more in the proportion of subjects remaining on spironolactone at Week 12, at $\alpha = 0.05$.

3 RANDOMIZATION AND BLINDING

At Screening Visit 4, eligible subjects will be randomized 1:1 to spironolactone + patiromer or spironolactone + placebo. Randomization will be stratified by the Visit S4 locally measured potassium value (4.3 to < 4.7 mEq/L or 4.7 to 5.1 mEq/L) and by history of Type 1 or 2 diabetes mellitus (Yes or No).

To minimize the potential for bias, subjects, site personnel, and sponsor and vendor staff will remain blinded to treatment assignments, with the exception of unblinded staff required for the development of the final randomization schedule and for production of unblinded materials for the Data Safety Monitoring Committee (DSMC). Drug safety staff may also be unblinded where this is necessary to comply with regulatory requirements.

For production of DSMC materials, an unblinded sponsor biostatistician and unblinded sponsor programmer(s) will be identified.

The final randomization schedule will be produced by unblinded staff at Endpoint, the IWRS vendor for this study, and will be reviewed by the sponsor DSMC unblinded biostatistician.

The study will be unblinded after database lock.

4 INTERIM ANALYSES

No interim efficacy analysis is planned for this study. Safety will be evaluated by the DSMC on an ongoing basis.

5 ANALYSIS SETS

5.1 Intent-to-treat Population (ITT)

The Intent-to-Treat (ITT) Population includes all subjects who have been randomized and have taken at least one dose of spironolactone and at least one dose of patiromer/placebo.

All efficacy analyses will be performed on the ITT population, analyzed by planned treatment group assignment. In addition, the primary and secondary endpoints will also be performed using the Per-protocol Population.

5.2 Per-protocol Population (PP)

The per-protocol population includes ITT subjects who have been compliant with dosing of both spironolactone and patiromer/placebo and who do not have any important protocol deviations (see Section 5.4).

Dosing compliance is defined as having taken 80-120% of the prescribed dose.

The primary and secondary endpoints will be performed using the PP Population, in addition to the ITT Population.

5.3 Safety Population (SAF)

The safety population will include all randomized subjects who have taken at least one dose of spironolactone or patiromer/placebo, analyzed according to the actual treatment received.

All safety analyses will be performed on the SAF population.

5.4 Protocol Deviations

Prior to database lock, all protocol deviations will be compiled. Important protocol deviations will be identified and used to determine, prior to database lock, the per protocol population.

The following deviations are considered, a priori, to be important protocol deviations:

- Violations of initial informed consent
- Enrolled in violation of the entry criteria
- Site errors in randomization assignment
- Administration of a prohibited medication to a study subject potentially affecting the primary and secondary efficacy endpoints
- Study subjects not discontinuing study medication when they met protocol criteria for stopping study treatment
- Dosing with study drug after a study subject's withdrawal from the study

6 ENDPOINTS AND VISIT WINDOWS

6.1 Efficacy Endpoints

6.1.1 Primary Efficacy Endpoint

The primary efficacy endpoint for this study is the proportion of subjects remaining on spironolactone at Week 12.

Subjects who terminate from the study early or discontinue study spironolactone prior to Week 12, for any reason, will be considered as not having remained on spironolactone until Week 12.

6.1.2 Secondary Efficacy Endpoint

The secondary efficacy endpoint is change from Baseline in AOBP SBP at Week 12 or last available AOBP SBP prior to addition of any new BP medications or increase from any baseline BP medications.

6.1.3 Other Efficacy Endpoints

The following other efficacy endpoints were specified by the protocol:

- Change in AOBP SBP from baseline to Week 12
- Potassium levels over time (measured both centrally and locally)
- Proportion of subjects with serum $K^+ \geq 5.5$ mEq/L
- Average daily dose and cumulative dose of spironolactone
- Time to discontinuation of spironolactone
- Change in albuminuria (urine albumin to creatinine ratio [ACR]) from baseline to Week 12
- EQ-5D-5L questionnaire results at Baseline and Week 12/ET

In addition to the endpoints specified in the protocol, the following additional endpoints will be examined:

- Change in AOBP SBP from baseline to Week 12 in the subgroup of patients remaining on spironolactone at Week 12
- Change in AOBP SBP/DBP over time

6.1.4 Exploratory Efficacy Endpoint

- Change in 7dHBP SBP/DBP over time

6.2 Safety Endpoints

Safety endpoints will consist of:

- Adverse events, including newly observed clinically significant physical examination abnormalities and events of interest (e.g. gastrointestinal events, renal events)
- Clinical laboratory test results and changes over time, including Spironolactone level and NT-pro-BNP.

- Vital signs
- ECG findings and changes
- Reasons for discontinuing patiromer/placebo/spironolactone
- Deaths

Adverse events will be coded using MedDRA 18.1.

6.3 Study Day and Visit Windows

6.3.1 Study Day

The first date of dosing with any study medication (either spironolactone or patiromer/placebo) will be used as the Reference Date for Study Day calculation.

The Study Day for date of first dosing is Day 1. The Study Day for all other study events is defined as follows:

- If a date is prior to the Reference Date, Study Day is defined as [date] - [Reference Date], so the Study Day for the day before date of first dose (typically the randomization day) is defined as Day -1.
- If a date is on or after the Reference Date, Study Day is defined as [date] - [date of randomization] +1; hence, the Study Day for the day after first dose is defined as Day 2.

6.3.2 Visit Windows

The protocol specified windows for scheduled visits are shown in the Schedule of Events (Appendix A).

Unless otherwise specified, analyses by visit will use the visit weeks reported in the database and include results collected at scheduled visits.

Analyses not limited to visits (e.g. incidence of laboratory test values within a given range, and time to event analyses), will include all available values of the variable of interest, irrespective of whether it was collected at a scheduled or unscheduled visit.

For central laboratory data, the visit information from the central laboratory will be used to determine whether a visit is scheduled or unscheduled.

6.3.3 Baseline

For all analysis variables, unless otherwise specified, baseline is the last non-missing value of the variable on or before the first dose of any study medication.

6.4 Key Considerations for Blood Pressure

Blood pressure is measured in three ways in this study:

- AOBP: Automated Office Blood Pressure
- SMBP: Subject-Measured Blood Pressure (performed at the study site using the HBP monitor)
- 7dHBP: 7-day Home Blood Pressure

The AOBP is an unwitnessed measurement taken at the clinic using an automatic office device that collects 3 measures of SBP/DBP. The mean of the three values is used for titration of study medication, and is the value that will be used for most analyses.

The SMBP is an unwitnessed measurement taken at the clinic using the subject's home blood pressure device. The home blood pressure device takes 3 readings automatically, and the mean of the three is used. If an AOBP is unavailable at a visit, for whatever reason, the SMBP will be used in its place to determine titration of study medications.

The HBP device is used by the subject outside the clinic to take measurements twice a day. At each sitting, 3 readings are taken automatically and uploaded to the Bioclinica database. The 7-day home blood pressure (7dHBP) is calculated from these measurements as follows:

1. Morning average = average of all measurements with time stamp midnight to before noon on given day
2. Evening average = average of all measurements with time stamp noon to before midnight on given day
3. Daily average = average of morning and evening averages
4. 7-day HBP (7dHBP) = average of daily averages for prior 7 days

The morning/evening averages include all values within the specified timeframes. If there are no valid readings during the morning time period, the morning average is missing, and the daily average will be based on the available values during the evening period, and similarly if there are no valid readings in the evening period. If there are no valid readings in either the morning or evening period, the daily average will be missing for that day. The 7dHBP is calculated using as many daily averages as are available for the previous 7 days. A valid 7dHBP requires that there be, at an absolute minimum, at least one valid reading for each of the prior 3 days. Readings taken with the HBP device while at the clinic are excluded from the calculation of the 7dHBP. Because the calculation requires averages of averages, rounding should not be done until the final 7dHBP result has been calculated.

For summaries of the 7dHBP by visit, the value of the 7dHBP at a visit will be calculated using the 7 days prior to the visit, and will not include any readings taken on the day of the visit.

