3.1.2 Double-Blind Treatment Period (12 weeks)

Randomization (Baseline – Day 0) Visit:

Subjects who meet all eligibility criteria at Visit S4 will be randomized on the same day to either patiromer or placebo treatment (1:1) with stratification based on the local potassium level at Visit S4 ($4.3 - < 4.7$ or $4.7 - 5.1$ mEq/L) and history of Type 1 or 2 diabetes mellitus (Yes or No). The S4 assessments will become the baseline assessments. A combined visit (S4/Randomization [Baseline/Day 0]) will be recorded for all randomized subjects.

All randomized subjects will be provided with detailed instructions for when to take spironolactone, patiromer/placebo, and other baseline medications after considering the subject's current medication regimen, patiromer/placebo instructions regarding administration, and subject preference (see Section 5.5.1). The subject will be instructed to begin taking study drugs (spironolactone and patiromer/placebo) on the following day (Day 1) and on the morning of their subsequent study visits to delay taking their blood pressure medications until office blood pressure measurements have been completed.

Treatment Period Visits (refer to Appendix A):

During the Double-Blind Treatment Period, study visits will occur at Week 1 (Day 8 ± 3 days), Week 2 (Day 15 ± 3 days), Week 3 (Day 22 ± 3 days), Week 4 (Day 29 ± 3 days), Week 6 (Day 43 ± 7 days), Week 8 (Day 57 ± 7 days), Week 10 (Day 71 ± 7 days), and Week 12 (Day 85 ± 7 days).

Patiromer/placebo treatment:

Patiromer/placebo will be taken at a starting dose of two packets once daily (QD). Based upon the treatment algorithm, patiromer/placebo will be increased in two-packet per day increments for local $K^+ > 5.1$ mEq/L in intervals of at least 1 week up to a maximum dose of six packets QD. For subjects with $K^+ < 4.0$ mEq/L, patiromer/placebo dose will be decreased by at least two packets per day. The minimum dose of patiromer/placebo is 0 packets. Patiromer/placebo should be taken with food, at least 3 hours before or 3 hours after administration of other concomitant medications including spironolactone. Refer to Appendix B for complete dosing and monitoring instructions.

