8.9.5 Exploratory Efficacy Analysis

7dHBP over time

Summaries of 7dHBP SBP/DBP will be provided at each visit and for change from Baseline, by treatment group. Summaries of change at each post-baseline time point will include only subjects who have non-missing values at baseline and at the post-baseline time point of interest.

Mean SBP/DBP and mean change from baseline will be presented graphically.

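### The Week 1 seven-day home blood pressure has no floor at first dose, so visits on Days 5 to 7 average in one to three pre-dose days

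*SAP*

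**What the plan says.** SAP 6.4 builds the home value from calendar-day averages: "7-day HBP (7dHBP) = average of daily averages for prior 7 days". For by-visit summaries, "the value of the 7dHBP at a visit will be calculated using the 7 days prior to the visit", and the value "will not include any readings taken on the day of the visit". For a visit on Day v the window is therefore Day v−7 to Day v−1.

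Two further rules apply. On missing days: "The 7dHBP is calculated using as many daily averages as are available for the previous 7 days". On validity: "A valid 7dHBP requires that there be, at an absolute minimum, at least one valid reading for each of the prior 3 days". Neither requires the days to be on treatment.

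On timing, protocol 3.1.2 says "study visits will occur at Week 1 (Day 8 ± 3 days"), which allows Day 5 to Day 11. SAP 6.3.1 says "The Study Day for date of first dosing is Day 1", and protocol 5.2 places that day directly after randomization. Protocol 7.3.2.1 has subjects measure at home twice daily through the run-in, so pre-dose readings will exist.

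On use, SAP 6.1.4 lists change in the seven-day home value as the exploratory endpoint, and SAP 8.9.5 says "Summaries of 7dHBP SBP/DBP will be provided at each visit and for change from Baseline, by treatment group", with graphs of the means.

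**The concern.** At the target day the rule works: a Day 8 visit uses exactly Days 1 to 7. At any earlier permitted day the window reaches back before first dose, and the resulting value is still reported as Week 1 change from baseline. How many run-in days enter depends only on scheduling.

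Nothing elsewhere corrects this. SAP 6.3.3 decides which value serves as baseline, but does not limit the readings that make up a later value. SAP 6.3.2 takes the visit week as recorded, so an early Week 1 visit is not reassigned. SAP 8.9.5 asks only that both values be non-missing.

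At stake is the first post-baseline point of the home blood pressure curve. If blood pressure falls on treatment, the error pulls that point toward zero. Some early visits would also use the same readings on both sides of the change.

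**Working it through.** The plan gives no figure of its own here, so the check is day counting in the protocol's numbering: randomization on Day 0, first dose on Day 1. (SAP 6.3.1 should be tidied separately. It fixes first dose as Day 1, but its formula for later dates counts from randomization. The count below does not use that formula.)

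**Formulas.** For a visit on Day v:

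- window = Days v−7 to v−1
- pre-dose days p = max(0, 8−v)
- share of the on-drug mean change kept = (7−p)/7, if all seven days are present and the pre-dose days have zero mean change from baseline
- days shared with baseline = overlap with Days −7 to −1, if baseline is the S4-visit value

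| Visit day | Window | Pre-dose days | Share kept | Days shared with S4 baseline |
|---|---|---|---|---|
| 5 | −2 to 4 | 3 | 4/7 = 57% | 2 |
| 6 | −1 to 5 | 2 | 5/7 = 71% | 1 |
| 7 | 0 to 6 | 1 | 6/7 = 86% | 0 |
| 8 | 1 to 7 | 0 | 100% | 0 |
| 9 to 11 | starts on Day 2 or later | 0 | 100% | 0 |

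If baseline were instead computed as of Day 1 (Days −6 to 0), the shared days for visits on Days 5, 6 and 7 would be 3, 2 and 1.

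**Average over the window.** The documents do not give the distribution of visit days, so two are assumed:

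- Uniform over Days 5 to 11: (3+2+1)/(7×7) = 6/49 = 12.2% of days pre-dose.
- Triangular, peaking at Day 8, with weights 1, 2, 3, 4, 3, 2, 1 (sum 16): (3×1 + 2×2 + 1×3)/(16×7) = 10/112 = 8.9%.

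**In mmHg.** Assume a constant 5 mmHg fall on every on-drug day. A Day 5, 6 or 7 visit then reports 5×4/7 = 2.9, 5×5/7 = 3.6 or 5×6/7 = 4.3 mmHg. The Week 1 mean loses 5×0.089 = 0.4 to 5×0.122 = 0.6 mmHg.

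**Missing days.** Because the rule averages whatever days are available, an individual value can be affected more. If only the prior three days and all pre-dose days have readings, the pre-dose share is 3/6 = 50%, 2/5 = 40% or 1/4 = 25% for visits on Days 5, 6 and 7.

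**Later visits.** Week 2 is Day 15 ± 3, so its earliest visit is Day 12, which uses Days 5 to 11. Week 2 and later in-window visits contain no pre-dose days.

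**The case against.** The strongest reply is that nothing inferential depends on this number. The home value is exploratory, and SAP 8.9.5 plans summaries and graphs with no model or test. Titration uses the automated office reading, or the subject's own on-site reading if that is missing (SAP 6.4). The primary analysis rests on spironolactone status and the secondary on office pressure. All of this stands.

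A reader might infer that the comparison between arms is biased. The documents do not support that. Both arms start spironolactone on Day 1, and protocol 1.2 expects any difference between arms to come from differing discontinuation, which can hardly have built up by Week 1. With similar visit timing in both arms, the rule dilutes a within-arm change in each and favours neither.

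A reader might also infer that the rule by itself distorts the onset of effect and that a floor would restore it. That goes too far. Protocol 1.1.2 says steady state is not reached until after 6 weeks of treatment, so Week 1 lies on a rising curve. A Day 5 visit limited to Days 1 to 4 would still tend to show less effect than a Day 11 visit using Days 4 to 10. Nor is a Day 8 window guaranteed to be wholly on drug, because a Day 1 morning reading may precede the first dose.

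Lastly, any trailing average blends across a transition, and a single uniform seven-day rule has the merit of simplicity. That is fair, but it does not justify run-in readings in a value reported as on-treatment change when a date filter removes them.

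**Conclusion.** The point holds and is minor. As written, SAP 6.4 puts 3, 2 or 1 pre-dose days into the Week 1 value for visits on Days 5, 6 and 7. That count follows directly from the documents. The fractions kept need complete readings and no mean change on the pre-dose days. The average loss rests on the assumed visit timing and the assumed 5 mmHg. The Day 5 case is the extreme of the permitted window and should not be read as the typical error. Overlap with baseline concerns Day 5 and Day 6 visits if baseline is the S4 value. It should not be claimed for every early visit.

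The correction is worth making because the rule yields a wrong value for permitted visits and is easy to repair. It does not bear on the trial's conclusions.

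**What to change.** Add to SAP 6.4: *For post-baseline visits, only daily averages dated on or after the date of first dose of any study medication are included in the 7dHBP.*

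The cost is this sentence and one date filter in the programming. Visits on Days 5, 6 and 7 would average at most 4, 5 or 6 days instead of 7, so those values are slightly noisier. In-window visits from Day 8 on are unchanged for subjects who start on Day 1.

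For subjects who start on Day 1 as instructed and attend in window, the three-day validity rule can still be met: a Day 5 visit needs Days 2 to 4, all on or after first dose. A later first dose or an out-of-window visit could leave too few eligible days. On a Day 3 visit, for example, the rule would look back to Day 0. The SAP should treat such a value as missing.

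Two limits remain. Day 1 readings taken before the first dose stay in, and early visits still reflect less time on drug. A footnote to the Week 1 summary can state both.
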